3. The third amendment regards modifying the consent form to include information related to the bi-weekly supervision calls our team provides to mentors. We also indicate that if we or their mentor is worried about the mentee's safety, we would be in communication with each other and with the mentee to ensure their safety and help address any pertinent issues.

Provide the rationale for the change(s)

1. The first change would allow us to better understand whether these factors influence the outcomes (e.g., is having the same diagnosis in mentor and mentee important to the success of the peer-mentorship intervention?).
2. The study acceptability questionnaire would be useful to better understand mentees' experience of the study, what they found helpful and what they liked or disliked about the intervention, and how this might influence outcomes.
3. The third change is already in place and the information is already transmitted verbally to participants, but we would like to add it to the consent form for clarity.

Comment on the extent to which the proposed change(s) alter or affect risks/benefits to subjects

1. There is a risk of unintentional disclosure of confidential information. This is outlined in the consent form and will be reviewed with mentors prior to mentors deciding whether to participate.
2. The proposed changes will not alter or affect the risks/benefits to the subjects.
3. The proposed changes will not alter or affect the risks/benefits to the subjects.

Comment on if the proposed change(s) require a modification to the Consent Form (CF)

1. We added a consent form for mentors

We would like to amend the consent forms to include the language: "Mentors attend bi-weekly mandatory phone supervisions with the research team. If your mentor is worried about your safety, they may reach out to us. If we are not able to reach you, we may reach out to your mentor. We may communicate with your mentor to discuss the situation and address an issue (e.g., if we have not heard from your provider)."

Procedures

To create the protocol summary form, first indicate if this research will include any of the following procedures

- Internet-based Data Collection or Transmission

Population

Indicate which of the following populations will be included in this research

- Children (ages 13-17)
- Adults

Research Support/Funding

Will an existing internal account be used to support the project?

No

Is the project externally funded or is external funding planned?

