indicate whether they wish to participate and consent will be documented by the EDRU RA. For participants who are 14 – 17 years old, parental consent and adolescent assent will be documented. We have requested a waiver for documentation of consent.

Describe Study Consent Procedures

As described above, potential participants and their parent(s) or legal guardian will hear the details of the screening process and study details described in one conversation.

1. For mentors, we propose to obtain consent by reviewing the consent form during a weekly supervision call with mentors (about 8 mentors participate on the call at one time). The PI will perform the consenting. Prior to this call, the PI will mention the study to mentors (during a *prior* weekly supervision call) and send them a copy of the consent form to view ahead of time. During the call, mentors will be instructed *not* to indicate whether they wish to participate, so that mentors do not feel social pressure to participate if they do not wish. Afterwards, a trained research assistant or study level clinician will contact each mentor separately to review any questions that the mentor has and find out if the mentor wishes to participate. Verbal consent will be documented for each mentor who chooses to participate.

Indicate which of the following are employed as a part of screening or main study consent procedures

Consent Form

Justification for Waiver or Alteration of Consent

Waiver of consent is requested for the following

We are requesting a waiver of consent to conduct telephone screenings.

We are requesting an alteration of consent to verbally review the consent with the participant by telephone and document verbal consent, rather than written consent.

Explain why your research can not be practicably carried out without the waiver or alteration
Contact and initial eligibility information is collected during the phone evaluation. Without access to this information, we would not be able to call a potential participant to arrange the next steps in study evaluation and participation.

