Aim 2: Evaluate the impact of intervention condition on eating disorder symptoms. Hyp 2a. Participants in peer mentorship will have greater reductions in eating disorder symptoms, measured using the Eating Disorder Symptom Inventory (EPSI), compared to both control conditions. Hyp2b: For individuals who meet criteria for current or past anorexia nervosa, individuals assigned to peer mentorship will be more likely to achieve or maintain a BMI ≥ 18.5 , compared to both control conditions. Hyp2c: For individuals who meet criteria for current or past bulimia nervosa or binge eating disorder, individuals assigned to peer mentorship will be more likely to abstain from bingeing/purging and bingeing episodes, respectively, compared to individuals in either control condition.

Aim 3: Evaluate the impact of intervention condition on total cost for eating disorder treatment. Hyp 3. Estimated total cost for eating disorder treatment, measured using the Healthcare Utilization Survey, will be lower among peer mentorship participants compared to both control groups at (i) post-treatment and (ii) one-year follow up.

Exploratory Aim: Evaluate characteristics of individuals participating as peer and social support mentors. Exploratory hypothesis: Mentor characteristics and similarity between mentee and mentor characteristics will not influence mentee outcomes (acceptability, eating disorder symptoms, and estimated treatment cost).

Inclusion/Exclusion Criteria

This section details your study sample(s) and addresses the requirement for risk minimization. You may choose to divide your sample by population (healthy controls vs. subjects) or by procedure (subjects who will have an MRI) and then define different sets of criteria for each.

For each sample, create or insert a table to describe detailed criteria for study inclusion and exclusion and the method you will use to ascertain each criterion. The method of ascertainment may describe tests, scales and instruments. When relevant, indicate the level of training of the person who will make the assessment (e.g. clinical interview by a psychiatrist).

Inclusion/Exclusion Criteria needs to be numbered and listed in outline form (see Table template below)

Mentees (Adolescents or adults with anorexia nervosa, bulimia nervosa, or binge eating disorder):

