**Note that all EDRU screens will be reviewed with a clinician (MD or PhD level) and if any criteria are in question, the clinician will speak directly with the potential participant by telephone.*

CRITERION	METHOD OF ASCERTAINMENT
Inclusion:	
1. Ages 14 – 45 years	Initial telephone interview with Project HEAL staff, confirmation during telephone screening with EDRU research team member (RA level or higher)*
2. Meets criteria for current or past anorexia nervosa, bulimia nervosa , or binge eating disorder (criteria met either presently or at time of entry into treatment for most recent treatment course)	Eating Disorder Assessment -5 (administered by EDRU RA* during telephone screening)
3. Recent (within past 6 m) discharge from inpatient, residential, or partial hospitalization program (PHP)	Initial telephone interview with Project Heal staff, confirmation during telephone screening with EDRU RA*
4. Involved in outpatient treatment at an appropriate level of care	Telephone screening with EDRU RA* and Documentation from primary outpatient clinical provider using Provider Form
5. Medical stability	Telephone screening with EDRU RA* and Documentation from primary outpatient clinical provider using Provider Form
6. Access to Smart Phone or computer to complete study assessments	Telephone screening
Exclusion:	
1. Evidence of needing specialized treatment for another medical or mental health condition or substance use	Telephone screening with EDRU RA*

Mentors:

Mentors in the peer-mentorship group are adults who have recovered from an eating disorder, while mentors in the social support group are adults who never had an eating disorder. All mentors are individuals recruited and trained by Project Heal to do volunteer work within their organization.

Inclusion/Exclusion criteria:

CRITERIA	METHOD OF ASCERTAINMENT
Inclusion	
1. Participating as a peer or social support mentor in Project HEAL intervention	1. Weekly telephone supervision with mentors
Exclusion	
1. Not being a mentor	1. Same as above

Study Procedures

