Peer mentors: Peer mentors receive 23 hours of training in an online “classroom” which includes completing readings, watching lectures, videos, film clips and role plays, as well as completing writing assignments. Training topics include: general information/history regarding peer mentorship interventions generally and Communities of HEALing specifically,

overview and in depth review of the [name] peer mentoring manual (8 keys), crisis responding, and training in human subjects research, including the specifics of the current study.

Social support mentors: Social support mentors receive training in the rational and procedures of the social support intervention, crisis responding, and general and study-specific research training components. Social support mentors do not receive training in core peer mentorship components. Social support mentor training is 4-5 hours.

In both groups, 2.5 hours of the mentor training is devoted to recognizing and responding to urgent/emergency situations. Training is coordinated by Project HEAL staff. The PI and Co-I will develop and lead training regarding research components.

Fidelity monitoring and supervision: Drs. [name] or [name] will provide supervision for mentors in both active conditions (peer mentorship, social support mentorship) twice per month. Mentorship and social support supervision will occur separately. Between scheduled supervision, mentors may contact Drs. [name] or [name] to discuss emergent questions/concerns. In urgent situations, mentors may contact the EDRU psychiatrist on call. In emergencies, mentors will be told to call 911. Over any period that a leader (mentor or volunteer) is providing the intervention, he/she will be required to attend the bi-monthly supervision and if necessary make up missed sessions. Supervision will focus on both clinical issues that arise during meetings with participants as well as treatment fidelity and adherence to the content of the intervention.

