Assessments: All participants will complete monthly assessments of eating disorder symptoms, eating disorder quality of life, and co-morbid psychiatric symptoms throughout the six month randomized phase and then again at a 12-month follow up time point. Participants assigned to the wait-list condition will also complete monthly assessments throughout the "open label" phase in which they are receiving mentorship. On a monthly basis, patients' treatment providers will be contacted in order to obtain the patient's current height/weight from which to calculate BMI. Patient questionnaires will be administered using Qualtrics, a HIPAA-compliant applications accessible by smart phone or computer. If, during participation in an intervention or wait-list condition, a participant is hospitalized or returns to a higher level of care (e.g., residential treatment, partial hospitalization), he/she may resume participation in the mentorship component of the study only with permission from his/her treatment provider (a new letter must be obtained from primary provider). **All participants will complete a questionnaire assessing study acceptability of the study at the end of the 6 months period of mentorship or as soon as their participation in the study ends (e.g., if a participant discontinues after 3 months, they will be asked to complete the survey at that time).**

Mentor Procedures:

Individuals participating as mentors will be asked if they are willing to allow the study team to utilize data previously collected as part of interviewing and training to be a mentor. This data includes demographic information such as age and gender, as well as diagnostic history, for the peer mentors. Mentors will be informed about the study during a supervision call with the PI of the study and Project HEAL staff. Prior to reviewing the consent form during the telephone call with all mentors, all mentors will be sent a copy of the consent form to review ahead of time. Mentors will be asked to then speak individually with one of the study team members (the PI, a trained RA or other study clinician) to indicate whether or not they wish to participate in the study.

The information collected as part of the process of interviewing to be a mentor will be sent in a de-identified format. The code linking mentor information with the identifier will be transmitted by phone to the study team. Mentors will also be asked to fill out a brief 4-question survey using Qualtrics.

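### Mentors who stopped mentoring before being approached have no route into the exploratory mentor analysis, so the pairs analysed may be selected, with unknown direction and size

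*Protocol*

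**What the plan says.** The mentor table under Inclusion/Exclusion Criteria has one inclusion criterion, "Participating as a peer or social support mentor in Project HEAL intervention", and one exclusion, not being a mentor. Both are ascertained by "Weekly telephone supervision with mentors".

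Consent uses the same channel. Under Describe Study Consent Procedures, "we propose to obtain consent by reviewing the consent form during a weekly supervision call with mentors"; afterwards "a trained research assistant or study level clinician will contact each mentor separately" to answer questions and record the decision. Mentor Procedures agrees: "Mentors will be informed about the study during a supervision call with the PI of the study and Project HEAL staff".

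Fidelity monitoring and supervision sets who must be on the calls: "Over any period that a leader (mentor or volunteer) is providing the intervention, he/she will be required to attend the bi-monthly supervision". (Call frequency is weekly in some sections and twice monthly in others. These should be reconciled, but the point here does not depend on it.)

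The mentor consent form was added by amendment. The amendment rationale says of the supervision arrangements, "The third change is already in place and the information is already transmitted verbally to participants", which indicates that mentoring was already under way.

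The Exploratory Aim predicts that "Mentor characteristics and similarity between mentee and mentor characteristics will not influence mentee outcomes", with acceptability, eating disorder symptoms and estimated treatment cost as the outcomes. The SAP's models contain only time, group and their interaction. Neither document defines an analysis set or a model for the mentor aim.

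**The concern.** The amendment wants to learn whether features such as a shared diagnosis matter to the success of mentorship. That requires pairs that went badly as well as pairs that went well. If a mentor can enter only while active and on the calls, a pair that ended before its mentor was approached contributes no mentor characteristics. Entry could then depend on the course of the pair, which is close to what the analysis is meant to explain. Mentees are matched on diagnosis where possible, so mismatched pairs may be few and each lost one would count.

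**Working it through.** The plan gives no power, effect size or pair-termination rate for this aim, so there is no figure to reproduce. The check has two parts.

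**1. Who is kept out**

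| Mentor's position when approached | Result under the text |
|---|---|
| Consented, pair ends later | Stays in; nothing removes a consented mentor |
| Pair ended, but has another mentee | Still participating and on the calls; can enter |
| Stopped, not yet approached | Does not meet the criterion, need not attend calls, no other route described |

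Only the third row is exposed. For these mentors:

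- Age, gender and diagnostic history come from interview and training records made before mentoring (Mentor Procedures). Only the 4-question survey would be new.
- Mentees are asked to go on completing questionnaires after meetings stop, and may decline (the discontinuation text and the safety procedures).
- Acceptability is collected at early exit (Assessments).

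The entry rule and the consent route are therefore what keep these pairs out. The listed grounds for early discontinuation include repeated missed sessions, non-attendance at outpatient treatment, and mismatch with more than one mentor. Several of these could plausibly relate to fit or to the mentee's course.

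**2. Which way a loss of pairs would push the result**

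Simulation with 2,000,000 pairs per scenario. Every parameter is an assumption.

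- Similarity s is 0 or 1 with equal probability. Outcome y = b·s + e, with e normal, SD 1; higher is better.
- Probability that a pair is kept = 1/(1 + exp(−L)), with L = 1 + g·(s − 0.5) + h·y + k·s·y.
- Effect = mean y in similar pairs minus mean y in dissimilar pairs.

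| Loss of pairs depends on | b | g | h | k | All pairs | Kept pairs |
|---|---|---|---|---|---|---|
| Neither | 0.4 | 0 | 0 | 0 | 0.40 | 0.40 |
| Similarity only | 0.4 | 1 | 0 | 0 | 0.40 | 0.40 |
| Poor outcome only | 0.4 | 0 | 1 | 0 | 0.40 | 0.35 |
| Poor outcome and dissimilarity | 0.4 | 1 | 1 | 0 | 0.40 | 0.22 |
| Poor outcome, similar pairs likelier to end | 0.4 | −1 | 1 | 0 | 0.40 | 0.48 |
| Poor outcome, more strongly in similar pairs | 0.4 | 0 | 0.3 | 1 | 0.40 | 0.56 |
| Poor outcome only, no true effect | 0 | 0 | 1 | 0 | 0.00 | 0.00 |
| Poor outcome and dissimilarity, no true effect | 0 | 1 | 1 | 0 | 0.00 | −0.14 |

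Between 26% and 31% of pairs were lost in these runs. The simulation drops every lost pair, whereas the trial would lose only those in the third row of the first table. It therefore shows which directions are possible; it does not estimate the size in this trial.

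**The case against.** The case against has four parts.

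- **Most mentors are reached.** Everyone delivering the intervention must attend supervision and make up missed sessions, and the decision is taken once, in an individual contact. A pair that fails after consent can be analysed. This stands, and it limits the point to mentors who stopped before being approached. The documents do not show that there were any.
- **A failed pair need not take the mentor off the calls.** Social support mentors may have several mentees, entry is rolling, and a mentor may receive another mentee. Mentors whose pairs completed six months are released from supervision too, so absence partly follows calendar time. This also stands. It makes the selection weaker and harder to sign, without closing the gap.
- **The criterion does not say currently.** True, but read with the exclusion and with ascertainment on supervision calls, it offers no means of finding or admitting a former mentor.
- **The aim is exploratory.** This stands, and it sets the priority.

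Two stronger readings are tempting. Because the hypothesis predicts no influence, a reader might infer that the losses favour it. The second table does not support that: the shift can be towards zero, absent or away from zero, and with no true effect a spurious one can appear. A reader might also fault Sample 2 for requiring 80 completers from 80 enrolled mentors. But mentors who decline or are not reached are never enrolled, and after enrolment the task is release of existing records plus a short survey, so that target is not shown to be wrong.

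**Conclusion.** The point holds in a limited form. As written, the entry rule leaves out mentors who stopped before being approached, and this may select the pairs available to the exploratory mentor analysis. Mentors who consented before their pair ended are not affected.

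Neither the direction nor the size of any bias can be determined from the documents. Both depend on how many pairs ended before approach, and on whether early ending related to mentee outcome, to similarity, or to both. A reader might try to size the bias from how many similar and dissimilar pairs last six months. That would not measure it, because the stated outcomes are acceptability, symptoms and cost, which the plan seeks to collect whether or not the pair lasts.

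The randomised comparisons are untouched. The plan is also silent on which mentor counts when a mentee is re-matched, but no particular rule follows from this point. This is a low-cost improvement to an exploratory aim.

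**What to change.** - Reword the mentor inclusion criterion to: *is, or at any time since the first randomisation has been, the mentor of a randomised participant*. Align the exclusion and the method of ascertainment with it, for example by using the matching records.
- Approach former mentors through the individual contact already described under Describe Study Consent Procedures, without requiring a supervision call first.
- For new mentors, seek consent at assignment, before the first meeting.
- Report the numbers matched, approached and consented, by whether the pair ended early.

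The cost is a protocol wording change and a few extra calls. Some former mentors will not respond, so selection may not vanish, but the reported counts would let a reader judge how much remains. Mentee procedures and the primary aims do not change.

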Eating disorders are serious mental illnesses associated with significant morbidity and high relapse rates. Patients are at especially high risk of relapse after leaving structured treatment (e.g., hospitalization). Adjunct interventions targeting patients' motivation and participation in treatment at these times may help more patients recover from eating disorders. Project HEAL is a non-profit organization whose mission is to reduce suffering caused by eating disorders. Project HEAL has developed a intervention in which patients with eating disorders are matched with peers who have previously recovered from an eating disorder, and mentors meet weekly with mentees to provide support, guidance, and serve as a model that recovery is possible. Project HEAL has asked the researchers at Columbia to help them evaluate the feasibility and effects of this intervention. Therefore, the purpose of the current study is to test whether peer-mentorship can help improve patients' eating disorder symptoms above and beyond their traditional treatment. The design of the study is a three-arm randomized controlled trial comparing peer mentorship to an active (social-support) and wait-list control conditions. Participants in the study will be randomized to one of the three conditions for six months. Wait-list participants will subsequently receive peer mentorship. Participants will complete assessments of their eating disorder symptoms at baseline, monthly throughout the course of the study, and one year after beginning the study. Outcomes will be compared between groups.

Description of Subject Population

Sample #1

Specify subject population

Individuals with a DSM-5 eating disorder

Number of completers required to accomplish study aims

80

Projected number of subjects who will be enrolled to obtain required number of completers

100

Age range of subject population

14 - 45

Sample #2

Specify subject population

Individuals serving as Project HEAL mentors

Number of completers required to accomplish study aims

80

Projected number of subjects who will be enrolled to obtain required number of completers

80

Age range of subject population

18 - 75

Gender, Racial and Ethnic Breakdown

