Eating Disorder Symptoms: Eating disorder symptoms will be assessed monthly using the Eating Pathology Symptoms Inventory (1). The Eating Pathology Symptoms Inventory (EPSI) is a self-report questionnaire that includes 45 items covering 8 subscales: Body Dissatisfaction, Binge Eating, Cognitive Restraint, Purging, Restricting, Excessive Exercise, Negative Attitudes toward Obesity, and Muscle Building. Each item is scored on a five-point Likert-style scale (0 = Never; 4= Often) to describe how well each item describes the participant's experiences. Scores are derived by summing responses across the questions included in each subscale. The EPSI is part of the Phynx Toolkit, a NHGRI/NIDA-sponsored catalog of recommended standard measures of phenotypes (symptoms) for use in biomedical research. To assess frequency of bingeing and purging episodes, BN and BED patients will be asked to report the average number of episodes/week experienced within the past month on each monthly report of symptoms.

Eating Disorders Quality of Life: Quality of life as related to the patient's eating disorder will be measured using the Eating Disorder Quality of Life assessment survey (2). The EDQOL is a 30-item measure assessing the impact of the eating disorder on psychological, physical/cognitive, financial and work/school domains of life. Participants indicate the extent to which the eating disorder has resulted in a variety of consequences within the past 30 days (e.g., "How often has your eating disorder led to low grades?" on a 5-point scale ranging from 1 = "never" to 5 = "always." Higher scores indicate higher levels of QOL impairment. The measure has been validated and demonstrates good psychometric properties.

Comorbid psychiatric symptoms: Anxiety symptoms will be measured using the State Trait Anxiety Inventory (STAI) (3).The STAI is a well-validated 20-item measure used to assess trait-level anxiety. Each item is rated on a scale of 0 – 2, with total scores ranging from 0 – 40. Depressive symptoms will be measured using the Patient Health Questionnaire-9 (PHQ-9), a 9-item self-report questionnaire commonly used in clinical practice. The PHQ has demonstrated good psychometric properties and has high sensitivity and specificity (4).

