Cover page

Official Title: Evaluation of the Communities of HEALing mentorship/support group program:
Assessment of preliminary efficacy

NCT number: NCT03317379

Document date: 3/23/2018

Statistical Analysis Plan

Intent-to-treat analyses will be used. Linear mixed models will be used to examine the relationship between group (peer, social support, wait list) and each outcome. Predictors in each model will be time, group, and their interaction. For all models, a random intercept will be included. The need for random slopes will be evaluated by examining model fit indices and testing the significance of the difference of the covariance estimate from zero. The peer group will be coded as the reference group to provide estimates and significance values for the difference between peer mentorship and each control condition.

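### Hyp 2a has no named EPSI score, alpha or success rule, leaving eight unadjusted chances at one primary claim; a false win over both controls could reach about 9–18% if only the wait list does worse, against about 2.5% with one pre-specified score.

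*Protocol*

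**What the plan says.** - **Protocol, Specific Aims and Hypotheses, Aim 2.** Hyp 2a stands under the primary aims and predicts "greater reductions in eating disorder symptoms, measured using the Eating Disorder Symptom Inventory (EPSI), compared to both control conditions". It names no subscale, total score or time point.
- **Protocol, Assessment Instruments, Eating Disorder Symptoms.** The EPSI "includes 45 items covering 8 subscales", and "Scores are derived by summing responses across the questions included in each subscale". No total or composite is defined. The measure is taken monthly.
- **SAP (a single paragraph).** "Linear mixed models will be used to examine the relationship between group (peer, social support, wait list) and each outcome". Each model contains time, group and their interaction. The peer group is the reference level so that the model gives "estimates and significance values for the difference between peer mentorship and each control condition". The SAP does not mention the EPSI or its subscales. It states no alpha, sidedness or multiplicity adjustment, and does not say how the two comparisons combine into a verdict on Hyp 2a.

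**The concern.** Hyp 2a is one claim about one construct, but the instrument as described delivers eight scores. Reading the SAP's reference to each outcome together with the scoring text gives eight models and two comparisons in each. If fewer were intended, the documents do not say which, so the choice could be made after the results are known. In both cases one favourable subscale could be offered as support for the hypothesis.

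The case that matters most is the one in which both mentored arms do better than the wait list but do not differ from each other. The social-support arm is there to separate peer mentorship from weekly contact in general. In that case the wait-list comparison is easily passed on every subscale and gives little protection. Eight chances at peer mentorship versus social support then drive the error, and the trial could report that peer mentorship is better than general support when it is not.

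**Working it through.** The plan states no error rate, effect size or power, so there is no figure of its own to reproduce.

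**Inputs from the documents.** Eight subscales; two comparisons sharing the peer arm; 80 completers in three arms (80/3 = 26.7, taken as 27 per arm).

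**Assumptions.** Two-sided 0.05 (0.025 in the favourable direction); 1:1:1 allocation, so the two contrasts correlate 0.5; equal correlation ρ between subscales, from 0.1 to 0.7; a win on any one subscale, against both controls, counts as support. t tests with 3×27 − 3 = 78 df stand in for the mixed-model contrasts. SD means the SD of whatever change measure is tested.

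**1. One score, all arms equal.** P(Z₁ > 1.96 and Z₂ > 1.96) at correlation 0.5 is 0.46%.

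**2. Eight scores, all arms equal.** If the subscales were independent, 1 − (1 − 0.0046)⁸ = 3.6%. Correlation lowers this to 2.3% at ρ = 0.7. If a different subscale could count for each control, the range is 2.9–5.7% (ρ from 0.7 to 0).

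**3. Upper limit when the wait list is far worse and peer mentorship equals social support.** The wait-list comparison always succeeds, so one score gives 2.5% and eight independent scores give 1 − 0.975⁸ = 18.3%. At ρ = 0.7 the figure is 9.5%.

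**4. In between.** Simulation with 27 per arm (40,000 replicates per cell), peer mentorship equal to social support, wait list worse by the stated amount on all eight subscales:

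| | 0 SD | 0.2 SD | 0.5 SD | 1.2 SD |
|---|---|---|---|---|
| Any of 8, ρ = 0.1 | 3.8% | 8.9% | 16.1% | 17.5% |
| Any of 8, ρ = 0.3 | 3.5% | 8.0% | 14.0% | 14.8% |
| Any of 8, ρ = 0.5 | 3.1% | 6.8% | 11.4% | 12.4% |
| Any of 8, ρ = 0.7 | 2.4% | 5.3% | 9.0% | 9.7% |
| One named score | 0.5% | 1.2% | 2.3% | 2.5% |
| Any of 8 at 0.05/8 | 0.2–0.3% | 0.5–0.8% | 1.3–2.0% | 1.7–2.4% |

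The last row is Holm's first step, with both controls beaten on the same subscale.

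**5. Detectable effects under the both-controls rule.** For one contrast, 80% power needs (1.99 + 0.84) × √(2/27) = 0.77 SD, but joint power against both controls at that effect is only about 69%. Joint power of 80% needs (1.99 + 1.17) × √(2/27) = 0.86 SD for one subscale. The mean of eight standardised subscales has SD √((1 + 7ρ)/8), which is 0.46 at ρ = 0.1 and 0.75 at ρ = 0.5. For an effect common to all eight, that gives 0.86 × 0.46 = 0.40 SD to 0.86 × 0.75 = 0.64 SD.

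**The case against.** The strongest reply is that the both-controls requirement is already strict. With all arms equal, the false-claim rate stays below 5% even with eight tries on the same subscale. That stands, and it is why no single inflated rate can be quoted. The higher figures need a wait list that is worse on all eight subscales, including Muscle Building and Negative Attitudes toward Obesity, although wait-list participants also receive outpatient treatment. The documents give no basis for the size or breadth of that deficit, nor for the correlation between subscales, so the result is a conditional range. Even so, a deficit of 0.2 SD already puts the rate at 5–9%.

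Three stronger readings are tempting and are not supported:

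- A reader might infer that the error rate exceeds the one the plan states. No alpha or error rate is stated; 0.05 is an assumption made here.
- A reader might infer that the SAP commits to testing all eight subscales. That is an inference from the scoring text; what the documents show is that the score is unspecified.
- A reader might quote the chance that any of the 16 two-sided tests reaches p<0.05, about 32–53% with all arms equal. That counts single comparisons and results against peer mentorship, so it does not describe a claim to beat both controls.

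The preliminary-efficacy label also carries weight. It lowers the severity but does not remove the gap, because Hyp 2a is a directional primary hypothesis and the SAP reports significance values for the comparisons it names.

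**Conclusion.** The point holds in conditional form. Neither document fixes the EPSI score, the alpha or the rule for declaring Hyp 2a supported. If any subscale may count at two-sided 0.05 with 27 per arm, a false win over both controls has probability of about 2–4% with all arms equal. When peer mentorship equals social support, it is about 5–9% with the wait list 0.2 SD worse and about 9–18% with it 0.5–1.2 SD worse (ρ from 0.7 to 0.1). One pre-specified score holds it at or below about 2.5% throughout. In relative terms the rate is roughly four to eight times that for one score (2.4/0.5 to 3.8/0.5 with equal arms; 9.7/2.5 to 17.5/2.5 at 1.2 SD). These figures rest on equal allocation, equal correlation between subscales and t tests standing in for the mixed model. The change should be made, but it is not critical for a trial of preliminary efficacy.

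**What to change.** Amend the SAP before anyone sees outcome data by arm:

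1. For Hyp 2a, name one EPSI score and one model contrast and time point. The randomised conditions last six months, so the time point needs to be set with that in mind.
2. State the alpha, and require p<0.05 against both controls. No further adjustment for having two controls is then needed.
3. Report the remaining subscales as secondary, with Holm adjustment.

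If no single score is preferred, keep all eight, apply Holm over the eight, and require both controls to be beaten on the same subscale. This holds the false-claim rate at about 2.5% or less.

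The average of the eight standardised subscales is one candidate for the single score, not the only one. It gives 80% power against both controls at about 0.40–0.64 SD (ρ = 0.1–0.5) for an effect common to all subscales, against about 0.86 SD for one subscale. It may be harder to interpret in a sample that mixes three diagnoses.

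The cost is SAP wording and no new data. What is lost is power for an effect confined to one or two subscales: an average dilutes it, and Holm sets it a stricter threshold. For example, with 27 per arm and a 0.8 SD effect, power for one comparison on one subscale falls from about 84% at 0.05 to about 58% at 0.05/8.
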